# 6.5.6.1 Nasal Inspection Abnormalities

On-treatment nasal inspection abnormalities will be summarized for each parameter as the number and percentage of subjects with abnormalities for the following parameters: nasal edema or nasal inflammation in either nostril; nasal edema in left nostril; nasal edema in right nostril; nasal inflammation in left nostril; nasal inflammation in right nostril. Percentages will be based on subjects with non-missing data for each parameter.

## 6.5.6.2 Nasal Inspection Evidence Shift from Baseline

Nasal inspection evidence shifts from baseline to an on-treatment abnormality will be summarized for each parameter (nasal edema in left nostril; nasal edema in right nostril; nasal inflammation in left nostril; nasal inflammation in right nostril) as the number and percentage of subjects in each evidence category (yes or no).

# 6.5.7 Safety Narratives

A by-subject listing of safety narrative subject identifiers will be provided for the following select events as columns: all deaths for enrolled subjects; all SAEs for enrolled subjects; all AEs leading to discontinuation of study therapy for treated subjects; on-treatment events of special interest for treated subjects: hepatic-related AEs; cardiovascular AEs; suicidality AEs; AST or ALT > 3 x ULN. The listing will flag subjects with events, as well as display total numbers of subjects with each event and any event in the first row.

### 6.5.8 Outcomes Research

Outcomes research endpoints are exploratory and will be assessed at 24 hours post-dose using the eDiary.

Analyses will be based on observed data without imputation and regardless of rescue medication use.

### 6.5.8.1 PoM

The PoM is a 5-point rating scale that measures the patient's preference of study medication to previous medications to treat migraine pain. The 5 preference categories are: much better, I prefer this medication; slightly better than the previous medication; about the same as the previous medication; slightly worse than the previous medication; and much worse, I prefer my previous medication.

Combined categories will include the following: (1) prefer study medication, defined as much better or slightly better; (2) prefer previous medication, defined as slightly worse or much worse.

PoM will be summarized as the number and percentage of treated subjects in each preference category (including combined categories) by as-treated treatment group and All BHV-3500.

Percentages for categories will be based on subjects with non-missing data, along with exact Clopper-Pearson 95% CIs for each percentage.

PoM will also be summarized analogously by as-randomized treatment group for mITT subjects: (1) overall; (2) by pain freedom outcome at 2 hours post-dose (responder, failure) for subjects who are included in the complete cases sensitivity analysis of pain freedom at 2 hours post-dose (see Section 6.3.3.1).

A by-subject listing of PoM will be provided for enrolled subjects.

### 6.5.8.2 MQoL

Impact of treatment on patient-reported quality of life is assessed using the MQoL Version 3.0, which is a 15-item questionnaire that has been validated in migraine patients to measure the short-term impact of treatment within 24 hours. The MQoL consists of 15 items across the following 5 domains: (1) work functioning; (2) social functioning; (3) energy/vitality; (4) migraine symptoms; (5) feelings/concerns.

Subjects will rate the negative effect of migraine headache and accompanying symptoms on each item on a 7-point scale, where 1 indicates maximum impairment of quality of life and 7 indicates no impairment.

There are 3 items within each domain. Each domain has a maximum score of 21 and a minimum score of 3. Items in domains are as follows:

- Work functioning: (1) ability to do normal everyday work, (2) ability to operate machinery or a motor vehicle, and (3) ability to stay alert.
- Social functioning: (1) interactions with people who are close to you \*, (2) interactions with other people \*, and (3) ability to enjoy life.
- Energy/vitality: (1) energy level, (2) ability to have a good night's sleep, and (3) mood.
- Migraine symptoms: (1) have throbbing head pain, (2) have increased sensitivity to light and/or noise, and (3) have nausea.
- Feelings/concerns: (1) feel upset about having migraine headaches, (2) feel physically uncomfortable, and (3) feel concern that your migraine medication wouldn't relieve your migraine headache symptoms.

Responses to items asterisked ("\*") are: a very great deal; a great deal; a good deal; a moderate amount; some; very little; and none. Responses to all other items are: all of the time; most of the time; a good bit of the time; some of the time; a little of the time; hardly any of the time; or none of the time.

The total score will be calculated as the sum of item scores to all 15 questions. All 15 item scores must be non-missing; otherwise, the total score will be considered missing.

Each domain score will be calculated as the sum of the 3 item scores pertaining to that domain. All 3 item scores must be non-missing; otherwise, the domain score will be considered missing.

MQoL total, domain, and item scores will be summarized by as-treated treatment group and All BHV-3500 for treated subjects as (1) continuous variables, and (2) the number and percentage of subjects in the following categories:

- Total score: 15 to 30, 31 to 45, 46 to 60, 61 to 75, 76 to 90, and 91 to 105
- Domain score: 3 to 6, 7 to 10, 11 to 14, 15 to 18, and 19 to 21
- Item score: 7-point scale categories defined previously
- Overall change since dose of medication: very much better; moderately better; a little better; no change; a little worse moderately worse; very much worse. Combined categories will include: (1) very much or moderately better; (2) not very much or moderately better, defined as the last 5 categories combined.

Percentages for categories will be based on subjects with non-missing data.

MQoL total, domain, and item scores will be summarized analogously by as-randomized treatment group for mITT subjects.

A by-subject listing of MQoL will be provided for enrolled subjects, and will present the total score, domain scores, and item scores for each domain.

### 7 CONVENTIONS

#### 7.1 General

### 7.1.1 Output Layout

All programmed outputs (i.e., TLFs) will be formatted and numbered according to the latest version of Biohaven Standard Outputs for CSRs.

A list of TLFs and corresponding templates will be presented separately in a mock TLF document corresponding to this SAP.

### 7.1.1.1 Time-to-Event Tables and Plots

Time-to-event endpoints will be summarized with KM tables displaying the following at each time interval:

- Number of subjects at risk, defined as those who did not have the event just prior to the start of the interval and who were not censored prior to the interval
- Number of subjects with events, defined as those who had the event for the first time during the interval
- Number of subjects censored, defined as those who did not have the event and whose censoring date/time is in the interval
- Cumulative probability of having the event with lower and upper CI limits, based on the KM product limit method.

Time-to-event endpoints will also be summarized with corresponding KM plots displaying 100 times the cumulative probability of having the event on the y-axis and time on the x-axis, including the number of subjects at risk at each time point below the x-axis.

Time-to-event distributions of endpoints will be summarized with the following descriptive statistics: number and percentage of subjects with events; number and percentage of subjects censored in or before the last time interval; number and percentage of subjects censored in the last time interval; median time to event with CI using the method of Brookmeyer and Crowley.

CI levels will be 98.3% for efficacy endpoints and 95% for all other endpoints.

# 7.1.1.2 By-Subject Listings

Unless specified otherwise, by-subject listings will be sorted by randomization status (randomized, not randomized), site-subject ID, and additional variables such as time points, as applicable. Listings will display site-subject ID and as-randomized treatment group.

By-subject listings will display site-subject ID and "(Age/Sex/Race)" stacked together in the same column using the following conventions:

- Age at informed consent will be displayed truncated to an integer.
- Sex will be displayed abbreviated as "F" for female and "M" for male.
- Race will be displayed abbreviated as "A" for Asian", "B" for Black or African American, "I" for American Indian or Alaska Native, "M" for multiple, "N" for Native Hawaiian or Other Pacific Islander, and "W" for White.

A footnote will describe race abbreviations as applicable, e.g., "Race: A = Asian, B = Black or African American, I = American Indian or Alaska Native, M = Multiple, N = Native Hawaiian or Other Pacific Islander, W = White". See Section 6.2.4.1 for multiple race. Missing age, sex, or race will be displayed as a single blank space.

Note that "(Age/Sex/Race)" will not be displayed in listings of randomization scheme and codes, batch numbers, and demographics.

Listings of non-study medications, eDiary migraine characteristics, safety parameters, and outcomes research parameters will show both study day and treatment day (see Section 7.5). Other listings will display study day only, if applicable.

# 7.1.2 Descriptive Statistics

For categorical variables, summary tabulations of the number and percentage of subjects within each category will be presented. If applicable, a "not reported" category for missing data will also be presented. Percentages will be displayed as: "<0.1" if 0 < percentage < 0.1; ">99.9" if 99.9 < percentage < 100; 0 count without a percentage; and rounded to 1 decimal place otherwise. Measures of variance (standard error [SE], CI) will be presented to 1 decimal place.

For continuous variables, descriptive statistics (e.g., n, mean, median, standard deviation (SD), minimum, and maximum) will be presented. The minimum and maximum will be presented with the same precision as the data. The mean and median will be presented with the precision of the data + 1 decimal place. Measures of variance (SD, SE, CI) will be presented with the precision of the data + 2 decimal places. For percent change from baseline, the minimum and maximum will be presented in 0 decimal places; mean and percentiles will be presented in 1 decimal place; and measures of variance in 2 decimal places. P-values < 0.0001 will be presented as "<0.0001". Otherwise, p-values will be presented in 4 decimal places.

## 7.1.3 Counting Rules

Frequency tables of the following endpoints will present the number and percentage of unique subjects with an event: significant protocol deviations; medical history; non-study medications; AEs; laboratory test shifts from baseline; vital sign and physical measurement abnormalities; ECG interpretation shifts from baseline and abnormalities; nasal inspection abnormalities. Thus, for these endpoints, multiple occurrences of the same event will be counted only once per subject.

Percentages in frequency tables will be calculated against the number of subjects in the group (i.e., sample sizes in column headers), unless specified otherwise. For safety findings and OR endpoints, percentages will be calculated on a subset of subjects as follows:

- In analyses of the worst abnormality or category in an analysis period, subjects must have a non-missing measurement in the analysis period to be included for a given parameter.
- In shift from baseline analyses of an analysis period, subjects must have a non-missing measurement at baseline and in the analysis period to be included for a given parameter.

# 7.2 Subgroups

Triptan non-responders are identified using the Prior Triptan Response CRF, which captures reasons for discontinuing triptans taken historically. The definition of triptan non-responder is based on the number of triptans that a subject failed for efficacy reasons. For each triptan and route of administration, the 4 efficacy-related questions are as follows:

- The treatment took too long to relieve my headache pain.
- The pain returned after it was relieved within 24 hours
- The treatment did not relieve my other symptoms (nausea, sensitivity to light or sound, for example).
- I could not count on this treatment to relieve my pain and symptoms every time.

Responses to each question are "most or all of the time", "some of the time", and "rarely". A subject is considered to have failed a drug for efficacy reasons if they responded "most or all of the time" to any of the 4 questions.

A triptan non-responder is defined as any subject that fails 2 or more molecular entities for efficacy reasons. To be considered a failure for a molecular entity, the subject must have failed on all routes of administration that the subject tried for the molecular entity.

## 7.3 Derived Dates

Derived dates are defined as follows:

- Study drug start date/time: Earliest study medication date and time from the eDiary Migraine Report or Study Medication Intake Report (see Section 7.6.3.1). This date is used to define analysis periods.
  - o eDiary Migraine Report
    - If the subject answered "yes" to taking study medication mistakenly already, then the following conventions will be applied depending when drug was reported taken:
      - Today: study drug start date will be set to the finding date, and the study drug start time will be set to the time of study medication taken, if available.
      - Yesterday: study drug start date will be set to the finding date -1 day, and study drug start time will be set to the time of study medication taken, if available.
      - Other: study drug start date will be set to the date of study medication taken, if available.
    - Otherwise, if the subject answered "no" to taking study medication mistakenly already and answered "yes" to confirming having taken study medication, then the study drug start date/time will be set to the finding date/time.
  - o Study Medication Intake Report: Study medication date/time.
- Rescue medication start date/time: Earliest rescue medication date/time (see Section 6.2.5.2). Missing time is considered to be earlier than non-missing time on the same date.
- Imputed rescue medication start date/time: This will be used only for time-to-event efficacy analyses in Section 6.3.5.2, and not for time to rescue medication use analyses in Section 6.3.4.3.
  - o If the rescue medication start date and time are both not missing, then the imputed rescue medication start date/time will be set to the rescue medication start date/time.
  - If the rescue medication start time is missing and the rescue medication start date is
    equal to the study drug start date, then the imputed rescue medication start date/time will
    be set to the study drug start date/time.
  - Otherwise, if the rescue medication start time is missing and the rescue medication start date is equal to a post-dose eDiary finding date with non-missing efficacy data, then the imputed rescue medication start date/time will be set to the first eDiary finding date/time corresponding to non-missing efficacy data.
  - Otherwise, if the rescue medication start time is missing and rescue medication start date is equal to the study drug start date + 1 day, then the imputed rescue medication start

date/time will be set to the study drug start date/time + upper bound of the *X*-hour analysis window (see Table 5).

• Last contact date: (1) Complete death date, if it exists; (2) otherwise, the maximum complete date of the following: AE start/stop; ECG; eDiary finding; eDiary study drug start; informed consent; IWRS randomization; laboratory collection; non-study medication start/stop; physical measurement; procedure; rating scale; questionnaire; study completion/discontinuation from Study Exit Status CRF; vital sign; visit.

No date imputations are performed on these derived dates. Complete dates are those with valid, non-missing day, month, and year.

## 7.4 Analysis Periods

Analysis periods are defined as follows:

- Pre-treatment: measurement date/time at or before the study drug start date/time. This period is used to derive baseline values and to assess pre-treatment endpoints.
- On-treatment: measurement date/time after the study drug start date/time. Note that AEs with imputed start date equal to the study drug start date are part of this period.
- On-study: measurement date/time after the randomization date/time.

See Section 7.3 for derived dates for determining analysis periods.

If measurement time is missing or not collected for a parameter, then the measurement date will be compared to the derived date.

# 7.5 Analysis Visit Windows

Study days are calculated from the IWRS randomization date as follows:

- Measurement date randomization date + 1, if measurement date ≥ randomization date
- Measurement date randomization date, if measurement date < randomization date.

Treatment days are calculated from the study drug start date as follows:

- Measurement date study drug start date +1, if measurement date  $\geq$  study drug start date
- Measurement date study drug start date, if measurement date < study drug start date.

Analysis windows for safety and outcomes research parameters are presented in Table 4.

For longitudinal analyses of safety and outcomes research parameters, the end of treatment analysis visit window is defined as measurement date/time > study drug start date/time.

# Table 4: Analysis Windows for Safety and Outcomes Research Parameters

Evaluation	Analysis-Specified Interval
Screening	≤ Study Day -1
Randomization	Study Day 1
Post-Randomization	≥ Study Day 2

See Section 7.6.3.2 for efficacy analysis windows.

## 7.6 Domain-Specific Derivations

### 7.6.1 Adverse Events

### 7.6.1.1 Imputed AE Start Dates

Imputed AE start dates will be used to classify AEs in analysis periods, and to determine LFT elevations concurrent with AEs of interest.

Complete dates are those with non-missing day, month, and year that are valid and consistent with the standard international calendar.

- Examples of complete dates: 01JAN2013, 31DEC2013;
- Example of non-complete dates: missing, 31FEB2013, MAY2013, 2013, "unknown", "ongoing", "continuing", "NA".

Partially complete dates are those with either (1) missing day with complete month and year, or (2) missing day and month with complete year. Examples: MAY2013, 2013.

To derive the imputed AE start date and numeric imputed start date flag, the following algorithm is used if the investigator term is non-missing:

- 1. If the reported start date is complete, then the imputed start date is set to the reported start date and the numeric imputed start date flag is set to 0 (No).
- 2. If the reported start date is partially complete then the following algorithm is used:
  - a. Calculate a surrogate date as the first complete date from the following list (in order of precedence):
    - i. First active study medication date of any study medication;
    - ii. Informed consent date;
    - iii. Visit date corresponding to the visit at which the event was reported.

If a complete date is not available for any of these 3 dates, then the surrogate date is set to missing.

- b. Calculate the derived date as the earliest possible date:
  - i. If only year is provided, then set the derived date to January  $1^{st}$  of that year. e.g.,  $2004 \Rightarrow 01$ JAN2004

- ii. If year and month are provided, then set the derived date to the first day of the month. e.g., AUG2004 => 01AUG2004
- 3. Compare the derived date with the surrogate date as follows:
  - a. If (1) the derived date is on or after the surrogate date or (2) the surrogate date is missing, then set the imputed start date to the derived date.
    - e.g., surrogate date = 05JAN2004, partial date = SEP2004, derived date = 01SEP2004 => imputed start date = 01SEP2004
  - b. If the derived date is before the surrogate date and the surrogate date is consistent with the partial date provided for the start date, then set the imputed start date to the surrogate date.
    - e.g., surrogate date = 05JAN2004, partial date = JAN2004, derived date = 01JAN2004 => imputed start date = 05JAN2004
  - c. If the derived date is before the surrogate date and the surrogate date is not consistent with the partial date provided for the start date, then set the imputed start date to be the latest possible date based on the partial start date information provided.
    - i. If only year is provided, then set the imputed start date to December 31st of that year. e.g., surrogate date = 05JAN2004, partial date = 2003, derived date = 01JAN2003, imputed start date = 31DEC2003
    - ii. If year and month and provided, then set the imputed start date to the last day of the month.
      - e.g., surrogate date = 05JAN2004, partial date = DEC2003, derived date = 01DEC2003, imputed start date = 31DEC2003

The numeric imputed start date flag is set to 1 (Yes).

- 4. If the reported start date is not complete and not partially complete, then the imputed start date is set to the first complete date from the following list (in order of precedence):
  - a. First active study medication date of any study medication;
  - b. Informed consent date;
  - c. Visit date corresponding to the visit at which the event was reported.

If a complete date is not available for any of these 3 dates, then the imputed start date is set to missing and the numeric imputed start date flag is set to 0 (No). Otherwise, the numeric imputed start date flag is set to 1 (Yes).

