¹ Screening Phase will be 3 - 28 days. Subject should be entered in the IWRS once they sign the informed consent form to obtain their study subject identification code.

²The **Baseline**/ **Randomization Visit** may only occur *after* all screening procedures are completed and the subject meets all inclusion/exclusion criteria. If the subject does not meet all eligibility requirements, the subject should be screen failed in the IWRS.

³ Subjects will use their assigned eCOA handheld device to answer questions about their migraine symptoms upon experiencing a moderate or severe migraine headache. The subject will administer study drug or matching placebo if the following criteria are met: 1) the headache remains moderate or severe; 2) the subject has completed all required migraine assessment questions in the handheld, including their current most bothersome migraine symptom, and 3) the subject has not already taken prohibited medications (see protocol section 5.4).

⁴ Subjects should keep track of their concomitant and rescue medications on the appropriate study paper diary provided throughout the study. These diaries should be returned to the investigational site for review and electronic data capture (EDC) entry.

⁵ The randomization visit is considered day 1 out of the 45 days subjects have to treat and report a migraine in their handheld device. Subjects will be randomized in the IWRS and will be stratified by answering "yes" or "no" to prophylactic migraine medication use in the IWRS.

⁶Nasal inspection – The nasal passages and turbinates will be visually inspected with a nasal speculum or otoscope at the screening, baseline and end of treatment visits to detect evidence of nasal inflammation or edema.

⁷ Height will only be captured at the Screening Visit. Weight, body temperature, respiratory rate, blood pressure and heart rate will be collected at all time points where indicated. Sitting arterial systolic and diastolic blood pressure and pulse rate will be measured.

- ⁸ SAEs are reported from the time of signed informed consent and non-serious AEs are reported from baseline. All ongoing non-serious AEs and SAEs will be followed to resolution or until the Investigator deems there will be no further status change. SAEs that occur during the treatment period should be reported to site in real time. Non-serious AEs that occur during the treatment period should be reported to the site at the EOT.

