# 7.6.2.1 Imputed Non-Study Medication Start Dates

To derive the imputed medication start date and numeric imputed start date flag, the following algorithm is used if the reported medication is non-missing:

- 1. If reported start date is complete:
  - o Imputed start date is set to reported start date.
  - o Numeric imputed start date flag is set to 0 (No).
- 2. If reported start date is partially complete:
  - Imputed start date is set to the earliest possible date based on the partial start date information provided.

```
e.g., SEP2018 => 01SEP2018, 2018 => 01JAN2018
```

- Numeric imputed start date flag is set to 1 (Yes).
- 3. If reported start date is not complete and not partially complete then do if informed consent date is complete then do if reported end date is at or before informed consent date then do if birth date is complete then do imputed start date is set to birth date

```
numeric imputed start date flag is set to 1 (Yes)
      else do (i.e., birth date is not complete)
       imputed start date is set to missing
      numeric imputed start date flag is set to 0 (No)
      end
   else if reported end date is after informed consent date then do
      imputed start date is set to informed consent date
     numeric imputed start date flag is set to 1 (Yes)
   end
  end
  else do (i.e., informed consent date is not complete)
   if birth date is complete then do
     imputed start date is set to birth date
     numeric imputed start date flag is set to 1 (Yes)
   end
  else do
   imputed start date is set to missing
   numeric imputed start date flag is set to 0 (No)
  end
 end
end
```

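### SAP 7.6.1.1 imputes incomplete AE start dates without checking the stop date, so an event known to have ended before dosing can be counted as on-treatment and usually as a TEAE

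*SAP*

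**What the plan says.** SAP 7.6.1.1 keeps a complete AE start date. For a partial date ("If the reported start date is partially complete then the following algorithm is used") it forms two dates: the earliest date the partial entry allows, and a surrogate. The surrogate is the first complete date among the study medication date ("First active study medication date of any study medication"), the consent date and the reporting visit date.

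- **Step 3b**, when the earliest possible date precedes the surrogate: if "the surrogate date is consistent with the partial date provided for the start date, then set the imputed start date to the surrogate date".
- **Step 4**, when nothing usable was reported: "If the reported start date is not complete and not partially complete, then the imputed start date is set to the first complete date" in the same list of three.

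The AE stop date appears in none of the steps.

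The imputed date then decides classification. SAP 7.4 defines the on-treatment period and adds that AEs "with imputed start date equal to the study drug start date are part of this period". SAP 7.6.1.2 assigns an AE to a period by imputed start date alone. SAP 7.6.1.3 calls an AE treatment-emergent if, for that subject and preferred term, its first occurrence is on treatment, or it worsened, or it newly became serious. None of these sections excludes an event that had already ended.

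**The concern.** Assigning an event of unknown timing to treatment is an ordinary conservative convention. It stops being defensible when the stop date shows that the event was over before exposure. The rule then produces a record that starts after it ends, and the event moves from the pre-treatment tables (SAP 6.5.1.2) to the on-treatment tables (SAP 6.5.1.3).

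The design leaves room for such events. Protocol Table 1, footnote 8, states that "non-serious AEs are reported from baseline", and dosing can follow up to 45 days after randomization. The same footnote has non-serious events in the treatment period reported at the End of Treatment visit, itself due 7 (+2) days after dosing. Recall over several weeks is one way for the day of onset to be lost. The frequency of AEs of at least moderate intensity is a stated, exploratory, objective.

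**Working it through.** **Inputs.** The steps are those of SAP 7.6.1.1, with classification by SAP 7.4, 7.6.1.2 and 7.6.1.3. Stop dates are available: SAP 7.3 uses them for the last contact date.

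**The plan's own examples.** Coding steps 1 to 4 reproduces all four worked examples (3a, 3b, 3c-i, 3c-ii). The one for 3b is: "e.g., surrogate date = 05JAN2004, partial date = JAN2004, derived date = 01JAN2004 => imputed start date = 05JAN2004".

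**Adding a stop date.** Keep dosing at 05JAN2004 and let the event end on 03JAN2004, as the first record of its preferred term.

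| Reported start | Step | Imputed start | Class as written | With stop-date check |
|---|---|---|---|---|
| JAN2004 | 3b | 05JAN2004 | on-treatment, TEAE | 03JAN2004, pre-treatment |
| 2004 | 3b | 05JAN2004 | on-treatment, TEAE | 03JAN2004, pre-treatment |
| missing | 4 | 05JAN2004 | on-treatment, TEAE | 03JAN2004, pre-treatment |
| DEC2003 | 3c | 31DEC2003 | pre-treatment | unchanged |
| 2003 | 3c | 31DEC2003 | pre-treatment | unchanged |
| 02JAN2004 | 1 | 02JAN2004 | pre-treatment | unchanged |

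In the first three rows the start falls 2 days after the event ended. With start AUG2019, stop 05AUG2019 and dose 20AUG2019, step 3b gives 20AUG2019, which is 15 days after the end. The four SAP examples carry no stop date, so the check leaves them unchanged.

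**Partial stop dates.** With start missing, stop JUL2019 and dose 20AUG2019, step 4 gives 20AUG2019. The latest possible stop is 31JUL2019, so the event was certainly over. A check limited to complete stop dates would miss it. With start and stop both AUG2019, the latest possible stop is 31AUG2019, and the event properly stays on-treatment.

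**Size.** The documents give neither the rate of pre-dose AEs nor the rate of incomplete dates, so this is an illustration. Treated subjects: 4 × 380 = 1,520 (SAP 5). Assume 5% have one pre-dose AE: 0.05 × 1,520 = 76. Assume 2% to 10% of these meet the full condition: 0.02 × 76 = 1.5 and 0.10 × 76 = 7.6, so about 2 to 8 events. As a share of treated subjects, 0.05 × 0.02 = 0.1% and 0.05 × 0.10 = 0.5%. If 10% had a pre-dose AE, the range would double to 0.2% to 1.0%.

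**Arm differences.** If a share p of each arm gains a false TEAE at random, a rate r becomes r + p(1 − r), and a difference d becomes (1 − p)d. With p = 0.5% and d = 5 points, 0.995 × 5 = 4.98 points.

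**Liver-test overlap.** SAP 6.5.2.2 pairs an ALT or AST above 3 × ULN with selected AEs whose imputed start is within 7 days of the sample, both in the same period. A pre-dose event moved to the dosing date falls within 7 days of an End of Treatment sample drawn up to 7 days after dosing, so it can be paired wrongly.

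**The case against.** The strongest reply is that the gap is narrow and errs against the drug. It needs a wholly missing start, or a partial start whose month or year includes the dosing date, together with a stop known to precede dosing. Imputed dates are flagged, and SAP 6.5.1 lists every AE by subject with TEAEs marked, so affected records can be found. The AE tables give counts and percentages with no between-arm test. All of this stands and limits the importance of the point. It does not justify a rule that yields a start after the stop.

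A reader might infer more than the documents support:

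- **That every affected event is a false TEAE.** Under SAP 7.6.1.3, one whose preferred term was already recorded pre-treatment at equal or worse severity is on-treatment but not a TEAE, unless it newly became serious.
- **That differences between arms are materially diluted.** With equal misclassification the risk difference barely moves, as shown above; ratios move towards 1.
- **That these events all enter the related-AE table.** SAP 6.5.1.1 counts an event as related if the relationship is missing, unlikely, possible or related. Imputing a date does not alter that field, so an event rated unrelated stays out.
- **That the medication rule already has the same safeguard.** SAP 7.6.2.1 does use an end date ("if reported end date is at or before informed consent date"), but only for a wholly missing start and against consent, not dosing. For a partial start it takes the earliest possible date without checking the end.

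One further ambiguity bears on scope. Read literally, "First active study medication date of any study medication" has no value for a placebo subject, whose surrogate would then be the consent date. With an assumed consent on 20DEC2003 and dosing on 05JAN2004, starts of JAN2004, 2004 and missing become 01JAN2004, 01JAN2004 and 20DEC2003, all pre-treatment. The error would then fall on BHV-3500 arms only. The documents do not establish that this is intended; active may simply mean study drug, placebo included.

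**Conclusion.** The point holds in a limited form. Under steps 3b and 4, an AE with an incomplete start compatible with the dosing date, or with no start at all, that is known to have stopped before dosing is given the dosing date. It is classed as on-treatment and, subject to the preferred-term condition above, as a TEAE. For placebo subjects this also requires that active study medication includes placebo.

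Absolute on-treatment and TEAE rates are slightly overstated, and the analysis of liver elevations concurrent with AEs can be affected. The count cannot be derived from the documents and is probably small; the 0.1 to 0.5 percentage points rest on the assumed 5% and 2% to 10%. Complete start dates, and partial dates from a month or year before dosing, are classified correctly. No efficacy result and no planned test is touched. It is a minor error in a stated rule, worth correcting because the correction is nearly free.

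**What to change.** Add to SAP 7.6.1.1, after steps 3 and 4: if the AE stop date, or the latest date that a partial stop date allows, is earlier than the imputed start date, set the imputed start date to that stop date. An event that ended before study drug is then pre-treatment under SAP 7.4. The same sentence removes start-after-stop records under step 3c, where the class does not change.

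In the surrogate list and step 4, replace the reference to active study medication with the study drug start date of SAP 7.3, stated to cover BHV-3500 and placebo; if something else is meant, say so.

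The cost is two short text edits and a line or two of code, using data already collected. Both belong in the SAP before database lock.
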